7.5 ASSESSMENT OF CAUSALITY

The Investigator must estimate the relationship between the investigational product and the occurrence of each AE or SAE by using his or her best clinical judgment. Elements to consider for this estimate include the history of the underlying disease, concomitant therapy, other risk factors, and the temporal relationship of the AE or SAE to the investigational product. The Investigator will also consult the Investigator's Brochure or product label for marketed products in estimating the relationship.

Because of reporting timelines, the Investigator might have minimal information to include in the initial SAE report. However, the Investigator must always make an assessment of causality for every SAE before the transmission of the SAE report. The

Investigator may change his or her opinion of the causality in light of follow-up information, with subsequent amendment of the SAE report. Causality assessment is a criterion used to determine regulatory reporting requirements and should not be left blank on the eCRF. The same applies to AEs that are to be processed as SAEs.

Table 6 provides some definitions to use in the assessment.

Table 6. Assessment of Causality of AEs

| Term | Definition |
|-------------------------------|---|
| Possibly related | The AE may be related to the investigational agent(s) or intervention: the AE has a temporal relationship to the administration of the investigational agent(s) or research intervention. |
| Unrelated (or not related) | The AE is clearly not related to the investigational agent(s) or intervention: the AE has no temporal relationship to the administration of the investigational agent(s) or research intervention, and follows no known or suspected pattern of response, and an alternative cause is present. |

7.6 EXPECTEDNESS OF SERIOUS ADVERSE EVENTS

An expected AE is one that is consistent with the known risk information described in the product label (if applicable) or the current Investigator's Brochure. The expectedness of an SAE will be assessed by the Medical Monitor and Sponsor on receipt of the initial SAE report.

7.7 REPORTING OF SERIOUS ADVERSE EVENTS

- 1. Any SAE occurring after the subject signs the ICF and the study drug has been administered, as described in Section 7.1, must be reported to the Sponsor's or designee's pharmacovigilance department by phone, fax, or e-mail within 24 hours of the time the Investigator becomes aware of the SAE (Table 7). Any SAE reported by phone should be immediately followed up with the submission of the completed SAE report form. Urgent reporting of SAEs is required for the following reasons:
 - a. To enable the Sponsor to fulfill the reporting requirements to the appropriate regulatory authority;

- b. To facilitate discussion between the Sponsor and the Investigator about appropriate follow-up measures (if necessary);
- c. To facilitate the Sponsor's rapid dissemination of information about AEs to other investigators or sites in a multicenter study;
- d. To facilitate reporting unanticipated problems involving risk to subjects to the institutional review board (IRB) or independent ethics committee (IEC).

Table 7. Timeline for Reporting SAEs

| Initial SAE Report | | Follow-up SAE Report | |
|--------------------|------------|----------------------|--------------------|
| Time Frame | Documents | Time Frame | Documents |
| 24 hours | SAE report | 7 days | Updated SAE report |

The SAE report will be completed as thoroughly as possible, including the following:

- Subject identification information;
- Event term;
- All available details about the SAE;
- Causality of each SAE;
- Signature of the Investigator.

The SAE report will be forwarded to the Sponsor's or designee's pharmacovigilance department within the designated time frames. If additional information to complete the SAE report is needed, the Investigator will not wait before notifying the pharmacovigilance department of the SAE. The SAE report will be updated by the Investigator when additional information is received.

7.8 FOLLOW-UP OF ADVERSE EVENTS AND SERIOUS ADVERSE EVENTS

After the initial AE or SAE report, the Investigator is required to proactively follow each subject and provide further information to the Sponsor about the subject's condition. All AEs and SAEs will be followed until the occurrence of one of the following:

- The condition resolves;
- The AE or SAE is considered not causally related to investigational product;
- The subject is lost to follow-up;
- The subject is followed for at least 30 days after the last dose of study drug (or other appropriate time frame);
- The subject starts another investigational product.

The appropriate SAE report will be updated once the SAE resolves, stabilizes, or is otherwise explained, or until the subject is lost to follow-up. The Investigator also will ensure that updates include any supplemental data that may explain causality of the SAE(s).

New or updated information will be recorded on a copy of the initial SAE report form; all incorrect data should be marked out (by a single line), initialed, and dated by the Investigator or designee, with the new information clearly recorded. The updated SAE report form will then be signed and dated by the Investigator and resubmitted to the Sponsor's or designee's pharmacovigilance department as outlined in Table 7.

7.9 LIVER ADVERSE EVENTS

The algorithm (Chalasani and Regev 2016) described in Table 8 will be used to monitor for drug-induced liver injury (DILI).

Table 8. Algorithm to Monitor for DILI

| Treatment Emergent ALT | Treatment Emergent Total Bilirubin (TB) | Liver Symptoms | Actions |
|--|--|----------------|---|
| Normal Baseline: ALT >2x ULN | Normal | None | Repeat ALT, AST, ALP, TB, in 2-5 days after receipt of the scheduled ALT results (Table 1). |
| Elevated Baseline: ALT >2x Baseline or >300 U/L (whichever occurs first) | Patients with Gilbert's syndrome: No change in Baseline TB | None | Follow up for symptoms. |

| Treatment Emergent ALT | Treatment Emergent Total Bilirubin (TB) | Liver Symptoms | Actions |
|---|--|---|---|
| Normal Baseline: ALT >5x ULN | Normal | None | Interrupt study drug. Initiate close monitoring and workup for competing etiologies. |
| Elevated Baseline: ALT >5x Baseline or >500 U/L (whichever occurs first) | Patients with Gilbert's syndrome: No change in Baseline TB | | Study drug can be restarted only if another etiology is identified and liver enzymes return to baseline. |
| Normal Baseline: ALT >2x ULN | TB >2x ULN | None | Interrupt study drug. Initiate close monitoring and workup for competing |
| Elevated Baseline: ALT >2x Baseline or >300 U/L (whichever occurs first) | Patients with Gilbert's syndrome: Doubling of direct bilirubin | | etiologies. Study drug can be restarted only if another etiology is identified and liver enzymes return to baseline. |
| Normal Baseline: ALT >2x ULN | Normal or elevated | Severe fatigue, nausea, vomiting, right upper quadrant pain | Interrupt study drug. Initiate close monitoring and workup for competing |
| Elevated Baseline: ALT >2x baseline or >300 U/L (whichever occurs first) | - | | etiologies. • Study drug can be restarted only if another etiology is identified and liver enzymes return to baseline. |

Note: Baseline is the average of the Screening and Baseline visit ALT measurements.

As described in Table 8, close monitoring of the subject must be initiated if certain signals of a possible DILI are detected. At a minimum, close monitoring includes:

- Repeating liver enzyme and serum bilirubin tests 2-3 times weekly. The frequency of retesting can decrease to once a week or less if abnormalities stabilize or if the study drug has been discontinued and the subject is asymptomatic.
- Obtaining a more detailed history of the subject's symptoms and prior or concurrent diseases.
- Obtaining a history of the subject's concomitant medication use (including non-prescription medications and herbal/dietary supplement preparations), alcohol use, recreational drug use, and special diets.
- Ruling out acute viral hepatitis types A, B, C, D, and E; autoimmune or alcoholic hepatitis; hypoxic/ischemic hepatopathy; and biliary tract disease.
- Obtaining a history of the subject's exposure to environmental chemical agents.
- Obtaining additional tests to evaluate the subject's liver function, as appropriate (e.g., INR, direct bilirubin).
- Considering gastroenterology or hepatology consultations.

At a minimum, the Medical Monitor should be consulted on events that may be considered DILI. Rechallenge is not recommended if it is determined that the subject has experienced DILI.

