The Investigator is responsible for all AE assessments. The Investigator and investigational site staff will note all AEs mentioned by the subject at Baseline and during study drug administration. All clinical complaints volunteered by or elicited from the subject during the study will be recorded on the appropriate page of the eCRF for the study period indicated (see Section 6.3.5). The subject will receive appropriate treatment and medical supervision for any AE that occurs.

All AEs judged to be clinically significant, including clinically significant laboratory abnormalities, will be followed until resolution. All AEs will be summarized in the annual report or more frequently if requested by the regulatory agency. Serious adverse events require special reporting in addition to documentation in the eCRF as described in Section 7.7.

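### Table 8's row 1 repeat panel omits direct bilirubin, the analyte on which row 3 interrupts drug in Gilbert's subjects: a narrow gap that is cheap to close

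*Protocol*

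**What the plan says.** Protocol Section 7.9 sets out a liver-injury algorithm in Table 8. Row 1 covers an ALT signal with no symptoms and normal total bilirubin (TB). For Gilbert's subjects the bilirubin condition is "No change in Baseline TB". The action is to "Repeat ALT, AST, ALP, TB, in 2-5 days after receipt of the scheduled ALT results" and to follow up for symptoms.

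Row 3 uses the same ALT thresholds and also requires no symptoms. For Gilbert's subjects its bilirubin condition is "Doubling of direct bilirubin", and its action is to interrupt study drug and start close monitoring.

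The note under the table says "Baseline is the average of the Screening and Baseline visit ALT measurements". It gives no corresponding reference value for direct bilirubin.

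Gilbert's subjects with raised TB may enrol if direct bilirubin, reticulocyte count and hemoglobin are normal (Protocol Section 3.3.2, note to exclusion 12). Direct bilirubin is in every scheduled on-treatment chemistry panel: the reduced panel at Weeks 2, 6 and 14 and the full panel at Weeks 10 and 18 (Protocol Tables 1 and 2, Section 5.1.3).

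**The concern.** With ALT and symptoms held equal, bilirubin alone decides whether a subject has tests repeated (row 1) or drug interrupted (row 3). For a Gilbert's subject the deciding analyte is direct bilirubin, and the row 1 repeat does not measure it. The sponsor foresaw these subjects, wrote separate criteria for them and put direct bilirubin in every scheduled panel, but left it off the one retest that a liver signal triggers. At stake is a later interruption of drug than the algorithm intends, in a subject with a rising ALT.

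**Working it through.** There is no figure in the plan to reproduce. The check sets the table's rows side by side and then does arithmetic on visit days.

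**1. Rows 1 and 3 for a Gilbert's subject**

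| | Row 1 | Row 3 |
|---|---|---|
| ALT, normal at baseline | >2x ULN | >2x ULN |
| ALT, elevated at baseline | >2x Baseline or >300 U/L | >2x Baseline or >300 U/L |
| Symptoms | None | None |
| Bilirubin | TB unchanged | Direct bilirubin doubled |
| Action | Repeat ALT, AST, ALP, TB | Interrupt drug |

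The row 1 repeat supplies nothing with which to test the row 3 bilirubin condition.

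**2. When the omission matters**

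- Doubling already present in the triggering sample: the scheduled panel shows it and row 3 applies at once.
- Doubling first present between the triggering sample and the repeat: the repeat does not show it. This is the gap.
- Doubling that starts after the repeat: the repeat would miss it with or without direct bilirubin on the list.

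The gap also requires that ALT stays below the row 2 threshold (>5x ULN, or >5x Baseline or >500 U/L) and that none of the row 4 symptoms appear. Either would interrupt drug anyway.

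**3. Wait until the next required direct bilirubin**

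Inputs: panels on days 14, 42, 70, 98 and 126, each ±3 days (Protocol Table 1); repeat 2-5 days after results arrive (Table 8). Turnaround from sample to result is not stated, so it is assumed.

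- Interval between panels: 42 - 14 = 28 days; with windows 28 - 6 = 22 to 28 + 6 = 34 days.
- Repeat, in days after the triggering visit = turnaround + 2 to 5.
- Wait = interval - day of repeat.

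| Assumed turnaround | Day of repeat | Wait, nominal visits | Wait, with windows |
|---|---|---|---|
| 1-3 days | 1 + 2 = 3 to 3 + 5 = 8 | 28 - 8 = 20 to 28 - 3 = 25 days | 22 - 8 = 14 to 34 - 3 = 31 days |
| 7 days | 7 + 2 = 9 to 7 + 5 = 12 | 28 - 12 = 16 to 28 - 9 = 19 days | 22 - 12 = 10 to 34 - 9 = 25 days |

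This applies to triggers at Weeks 2, 6, 10 and 14. After a Week 18 trigger there is no later panel, but dosing has ended.

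**4. TB as a backstop**

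If direct bilirubin doubles and indirect bilirubin is unchanged, TB rises by the starting direct value, a relative rise of direct/TB. The documents give no reference ranges. Taking the SAP Section 5.3.2 limit of 0.20 mg/dL as the direct ULN, and a TB just above an assumed ULN of 1.0-1.2 mg/dL, the rise is at most 0.20/1.2 = 17% to 0.20/1.0 = 20%. With an assumed direct ULN of 0.3 mg/dL it is up to 0.3/1.0 = 30%. Such a change may be noticed or may pass as variation, since Table 8 does not say how large a change counts. If it is noticed, the subject leaves row 1, but row 3 still calls for direct bilirubin.

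**5. Other provisions**

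The close-monitoring list names direct bilirubin only as an example of a discretionary test, and row 1 does not start close monitoring. Protocol Sections 5.1 (unscheduled visits), 6.3.4 (review of central laboratory results), 7.1 and 7.8 (follow-up of abnormalities and adverse events) and 8.1 (consulting the Medical Monitor) all allow earlier testing. None requires this analyte at the repeat.

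**The case against.** The strongest reply is that the case may be empty. It needs a Gilbert's subject, an asymptomatic ALT rise of limited size, a doubling that begins within days of the triggering sample, and no clinician who orders the test. That stands, and it keeps the point small.

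A second reply is that the repeat is not blind, because a changed TB takes the subject out of row 1 and applying row 3 then calls for direct bilirubin. In addition, "At a minimum, the Medical Monitor should be consulted on events that may be considered DILI", and a row 1 signal plausibly qualifies. This stands in part: these routes make an unattended wait of several weeks a worst case, but they rest on a small TB change being noticed or on discretion.

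A third reply is that adding the analyte has a clinical cost. Row 3 allows restart only if another cause is found and enzymes return to baseline. A rise from 0.1 to 0.2 mg/dL, which does not exceed the SAP's >0.20 mg/dL limit, would count as a doubling. Interruption might also leave a subject short of the 80 dosing days needed for the primary efficacy dataset (Protocol Section 9.2.2, SAP Section 4.1). On nominal days the fix could change that only for a Week 10 trigger: after a Week 2 or Week 6 trigger the next panel (day 42 or 70) also falls before day 80, and a Week 14 trigger (day 98) falls after it. This cost should be stated, but it is the protocol's own interruption rule applied sooner.

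A reader might infer that a doubling in a Gilbert's subject would go undetected, or that subjects would be harmed. The documents support neither. Scheduled panels measure direct bilirubin throughout treatment, so recognition may be delayed but is not prevented, and nothing in the documents shows that such a delay causes harm.

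**Conclusion.** The mismatch is real: the row 1 repeat cannot assess the criterion on which row 3 interrupts drug in Gilbert's subjects. It is confined to the sequence in step 2, and the number of subjects cannot be estimated from the documents; it is very small and may be zero. For such a subject the next required measurement comes roughly two to four weeks after the repeat. At nominal visits the wait is 16-25 days across the turnarounds tried, and 10-31 days at the extremes of the visit windows. The figures rest on the assumed turnaround and on nobody ordering the test sooner. The TB percentages rest on assumed reference limits. This is a cheap improvement to consider, not a flaw that threatens the trial.

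**What to change.** Add direct bilirubin to the row 1 repeat list in Table 8, at least for Gilbert's subjects. State that doubling is judged against the average of the Screening and Baseline direct bilirubin values, matching the note for ALT. Both values are already collected. The choice of reference matters at low levels: with 0.1 mg/dL at Screening and 0.2 mg/dL at Baseline, for illustration, doubling means 2 x 0.15 = 0.30 mg/dL against the average but 2 x 0.2 = 0.40 mg/dL against the last value.

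The cost is one more analyte on a sample already being drawn and a few words in the table. Row 3 interruption may also come earlier in a rare subject, including for a small absolute rise within the normal range.

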6.2.2 Efficacy Related Laboratory and Biomarker Assessments

A central laboratory will be utilized to perform efficacy related clinical laboratory and biomarker assessments as specified in Table 1 and Table 2 and as described in this section. Samples for laboratory and biomarker assessments performed at Baseline must be collected **prior to study drug dosing**. The Investigator or qualified designee must review the results of all central laboratory testing to assess subject eligibility at Screening and Baseline, as well as continued study participation for the duration of the Double-Blind Treatment Period. Procedures for sample collection and handling,

including the blinded reporting of any results, will be detailed in the central laboratory manual and/or SPM.

The following laboratory and biomarker assessments will be utilized as secondary efficacy measures:

Fasting glucose, HbA1c, HOMA-IR, serum triglycerides, LDL-c, and HDL-c will be utilized in this study to assess glucose metabolism, insulin resistance, and lipid metabolism. These measures are routinely performed in the management of metabolic abnormalities that underlie the pathogenesis of NAFLD, including dyslipidemia and T2DM, the latter of which is recognized as a risk factor for progressive hepatic fibrosis (Adams and Angulo 2006).

Aspartate aminotransferase and ALT are liver-associated enzymes that will be utilized in this study to assess liver biochemistry. These enzymes are markers of liver injury that may be useful surrogate measures of NAFLD and NASH, particularly in T2DM patients (Sanyal et al., 2015).

Pro-C3 and the ELF score are biomarkers that will be utilized in this study to assess liver inflammation and fibrosis. Pro-C3 is a neo-epitope of PIIINP, which has been reported to reflect the true formation of collagen and to potentially be an accurate biomarker for the formation of fibrotic tissue in the liver (Nielsen et al., 2013). The ELF score is a set of extracellular matrix markers that consists of TIMP-1, PIIINP, and HA, and has been reported to show good correlations with fibrosis stages in chronic liver disease (Lichtinghagen et al., 2013).

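### Protocol Table 8 prescribes no action for asymptomatic subjects with total bilirubin above 1× and up to 2× ULN, although at ALT >5× ULN it requires interruption on both sides of that band

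*Protocol*

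**What the plan says.** Protocol Section 7.9 states that Table 8 will be used to monitor for drug-induced liver injury. Each row combines an ALT level, a TB condition and a symptom status with an action. In the quotes below, vertical bars separate the columns. For a normal baseline ALT the four rows are:

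- **Row 1:** ALT above 2× ULN, TB normal, no symptoms. Repeat ALT, AST, ALP and TB in 2-5 days and follow up for symptoms.
- **Row 2:** "Normal Baseline: ALT >5x ULN | Normal | None | Interrupt study drug", with close monitoring, a workup for other causes and a limit on restarting.
- **Row 3:** "Normal Baseline: ALT >2x ULN | TB >2x ULN | None | Interrupt study drug", with the same accompanying measures as row 2.
- **Row 4:** "Normal Baseline: ALT >2x ULN | Normal or elevated | Severe fatigue, nausea, vomiting, right upper quadrant pain". Interrupt, with the same accompanying measures.

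Elevated-baseline subjects have their own ALT triggers. For row 2 the trigger is "Elevated Baseline: ALT >5x Baseline or >500 U/L (whichever occurs first"). For rows 1, 3 and 4 it is 2× Baseline or 300 U/L, again whichever comes first.

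Gilbert's subjects have their own TB conditions. Rows 1 and 2 give "Patients with Gilbert's syndrome: No change in Baseline TB". Row 3 gives "Patients with Gilbert's syndrome: Doubling of direct bilirubin".

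**The concern.** The three asymptomatic rows accept either normal TB or TB above 2× ULN. A subject without Gilbert's whose TB lies between these matches none of them, whatever the ALT. The table then gives a weaker instruction for a worse signal: compared with the same ALT at normal TB, adding a raised bilirubin takes the subject out of a row that mandates action.

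At row 2 ALT levels, what is missing is the interruption, the close monitoring (liver tests 2-3 times weekly at first), the workup and the restart limit. At row 1 ALT levels it is the 2-5 day repeat. After Week 2, scheduled chemistry is every 4 weeks, so without a prescribed retest the next scheduled result could be about 4 weeks away with dosing continuing. About 15 sites could handle the same ALT-bilirubin signal differently, in patients who already have liver disease.

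**Working it through.** No sample-size, power or alpha figure bears on this point. The check is to apply the table's conditions as written.

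**1. What normal means.** Row 4 admits TB that is normal or elevated, so the table treats these as different states. Exclusion criterion 12 (Section 3.3.2) likewise treats TB above ULN as out of range. Rows 1 and 2 are therefore read as TB ≤1× ULN.

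**2. Normal baseline ALT, no symptoms, no Gilbert's.** Rows matched:

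| ALT | TB 0.8× ULN | TB 1.5× ULN | TB 2.5× ULN |
|---|---|---|---|
| 3× ULN | row 1: repeat in 2-5 days | no row | row 3: interrupt |
| 6× ULN | rows 1 and 2: interrupt | no row | row 3: interrupt |

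The edges of the band are exact. At ALT 2.5, 4, 6 and 10× ULN, TB of 1.01, 1.5 and 2.0× ULN match no row, while 1.0× and 2.01× ULN do. With row 4 symptoms, every TB value leads to interruption.

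**3. Elevated baseline ALT, no symptoms, no Gilbert's.** The trigger is the lower of the two limits:

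- Row 2: min(5 × Baseline, 500 U/L). The 500 limit governs once Baseline exceeds 500/5 = 100 U/L.
- Rows 1 and 3: min(2 × Baseline, 300 U/L). The 300 limit governs once Baseline exceeds 300/2 = 150 U/L.

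The ULN of 40 U/L below is assumed, so that both baselines count as elevated:

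| Baseline ALT | Row 1 and 3 trigger | Row 2 trigger | Current ALT | TB 0.8× ULN | TB 1.5× ULN | TB 2.5× ULN |
|---|---|---|---|---|---|---|
| 80 U/L | 160 | 400 | 420 | interrupt | no row | interrupt |
| 80 U/L | 160 | 400 | 240 | repeat | no row | interrupt |
| 120 U/L | 240 | 500 | 520 | interrupt | no row | interrupt |

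The second line is 240/40 = 6× the assumed ULN but only 3× Baseline. In elevated-baseline subjects, ALT above 5× ULN does not by itself reach row 2, so the gap has to be stated at the row's own trigger.

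**4. Gilbert's, normal baseline ALT, no symptoms.** The three states are TB unchanged, TB changed with direct bilirubin at 1.5 times its earlier value, and direct bilirubin doubled. At ALT 3× ULN they match row 1, no row, row 3. At ALT 6× ULN they match rows 1 and 2, no row, row 3.

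**5. Is the band covered elsewhere?**

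- Sections 6.2.2 and 6.3.4: "The Investigator or qualified designee must review the results of all central laboratory testing", to judge eligibility and continued participation.
- Section 7.1: "All AEs judged to be clinically significant, including clinically significant laboratory abnormalities, will be followed until resolution".
- Section 7.8 requires follow-up of reported events, and Section 5.1 allows unscheduled visits.
- Section 7.9 asks for Medical Monitor consultation on possible drug-induced injury. Its close-monitoring paragraph refers back to Table 8, so it is not a separate trigger.
- Section 8.1 allows discontinuation on judgement.
- Section 7.11 gives a DSMB safety oversight.

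None of these sets an interruption, a retest interval or a restart limit for the missing band.

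**The case against.** The strongest reply is that the gap is narrow and unlikely to lead to inaction.

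- **Subjects already interrupted.** A subject stopped under row 2 stays stopped, because restart requires another cause to be identified and enzymes to return to baseline. A later TB rise to 1.5× ULN does not lift that. At row 2 ALT levels the gap applies only when TB is already raised as ALT first crosses the trigger. This stands and narrows the exposure; it does not close the gap.
- **Safeguards.** Every central laboratory result must be reviewed with continued participation in mind, and ALT above 5× ULN with raised bilirubin would plainly call for the Medical Monitor. This also stands. These are decisions on judgement, whereas a fixed algorithm exists to make action and timing uniform.
- **Meaning of normal.** It could be read as anything up to row 3's threshold. The table does not say so, and row 4's wording makes that reading strained. If it was the intent, the amendment simply writes it down.
- **Published source.** Section 7.9 attributes the algorithm to a publication. Whether the gap comes from there cannot be checked from the documents, but sites follow the protocol's text.
- **Rarity.** The case needs no row 4 symptoms, a triggering ALT and TB within one band. Its frequency is unknown.

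**Conclusion.** The concern holds and should be fixed. For asymptomatic subjects without Gilbert's, Table 8 leaves TB above 1× and up to 2× ULN without an action at every triggering ALT. At row 2 ALT levels the sequence across TB bands is interrupt, none, interrupt; at row 1 levels it is repeat, none, interrupt. Gilbert's subjects whose TB has changed without a doubling of direct bilirubin fall in the parallel gap.

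This rests on reading normal TB as within the reference range. Outside Gilbert's, exclusion criterion 12 makes a raised TB new since Screening. It need not be new since first dose, because Section 5.1.2 does not use the Baseline laboratory results for eligibility. The consequence is an inconsistent subject-safety rule, softened by discretionary safeguards. No endpoint or analysis is affected.

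**What to change.** In rows 1 and 2 of Table 8, replace the normal-TB condition with TB not more than 2× ULN and, for Gilbert's, direct bilirubin less than doubled. State that the stronger action applies when a subject meets more than one row. The conditions then meet row 3 without a gap (asymptomatic, no Gilbert's):

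| ALT level | TB normal | TB above 1× to 2× ULN | TB above 2× ULN |
|---|---|---|---|
| Row 2 trigger | interrupt | interrupt | interrupt |
| Row 1 trigger only | repeat in 2-5 days | repeat in 2-5 days | interrupt |

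The repeat in the middle cell of the lower line is a minimum; the sponsor's hepatology advisers may prefer a stronger action there.

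The cost is a short protocol amendment to two rows of one table, and possibly a few extra retests or interruptions. ALT, total bilirubin and direct bilirubin are already measured at every treatment visit (Section 5.1.3 and Table 2), so no scheduled test is added.

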6.3.4 Safety Related Laboratory Assessments

A central laboratory will be utilized to perform safety related clinical laboratory assessments as specified in Table 1 and Table 2 and as described in this section. Samples for laboratory assessments performed at Baseline must be collected **prior to study drug dosing**. The Investigator or qualified designee must review the results of all central laboratory testing to assess subject eligibility at Screening and Baseline, as well as continued study participation for the duration of the Double-Blind Treatment Period. Procedures for sample collection and handling, including the blinded reporting of any results, will be detailed in the central laboratory manual and/or SPM.

In addition to standard serum chemistry, lipid, hematology, and coagulation panels (see Table 2) conducted at specific visits throughout the study, samples to assess HIV and Hepatitis B/C, G6PD, and recreational drug use will only be collected at Screening to determine those factors that could render the subject unsuitable for the study or confound study results.

A local laboratory will perform serum pregnancy testing at Screening, Baseline, and at the Week 18 visit for all FOCP. A locally performed urine pregnancy test will also be done at Baseline. A local laboratory will perform FSH testing at Screening for all postmenopausal females.

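### Table 8 allows study drug to restart after a bilirubin- or symptom-linked liver interruption without requiring the bilirubin or the symptoms to recover

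*Protocol*

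**What the plan says.** Table 8 in Protocol Section 7.9 has four rows. The first calls for repeat tests and symptom follow-up. The other three interrupt study drug and start close monitoring and a workup for other causes. Each of those three ends with the same restart sentence: "Study drug can be restarted only if another etiology is identified and liver enzymes return to baseline".

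Below the table, close monitoring includes "Repeating liver enzyme and serum bilirubin tests 2-3 times weekly". The note to the table says "Baseline is the average of the Screening and Baseline visit ALT measurements". The section closes with "At a minimum, the Medical Monitor should be consulted on events that may be considered DILI" and with advice not to rechallenge once DILI has been determined.

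Elsewhere, Section 6.2.2 says the investigator or a qualified designee "must review the results of all central laboratory testing". Section 6.3.4 repeats that duty and ties it to "continued study participation for the duration of the Double-Blind Treatment Period". Section 7.1 says that AEs judged clinically significant, "including clinically significant laboratory abnormalities, will be followed until resolution".

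**The concern.** A restart rule should normally show that whatever caused the stop has gone away. Two of the three interruption rows act on a combination: raised ALT with raised bilirubin, or raised ALT with liver symptoms. The restart sentence asks for a cause and for enzyme recovery. It does not ask for the bilirubin to fall or the symptoms to clear.

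What is at stake is re-exposure of a subject after a possible DILI signal. Raised ALT together with raised bilirubin is a pattern that the protocol itself treats as more serious than the same ALT rise alone.

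**Working it through.** No sample size, power or event figure bears on this, so the check sets each trigger beside its restart condition.

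| Table 8 row | ALT trigger: normal baseline (elevated baseline) | Bilirubin | Symptoms | Action | Part of the trigger with no recovery criterion |
|---|---|---|---|---|---|
| 1 | >2x ULN (>2x Baseline or >300 U/L) | Normal | None | Retest, follow up | Not applicable |
| 2 | >5x ULN (>5x Baseline or >500 U/L) | Normal | None | Interrupt | None |
| 3 | As row 1 | TB >2x ULN; in Gilbert's syndrome, direct bilirubin doubled | None | Interrupt | Bilirubin |
| 4 | As row 1 | Normal or elevated | Severe fatigue, nausea or vomiting, or right upper quadrant pain | Interrupt | Symptoms, and bilirubin if elevated |

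**Step 1: what causes the interruption.** Rows 1, 3 and 4 share the same ALT threshold. With normal bilirubin and no symptoms the action is a retest. With raised bilirubin or symptoms it is an interruption. So the added component is what stops the drug, and it is the component without a recovery criterion. This holds in 2 of the 3 interruption rows.

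**Step 2: whether liver enzymes could include bilirubin.** The close-monitoring text names the two separately: "Repeating liver enzyme and serum bilirubin tests 2-3 times weekly". Section 6.2.2 describes AST and ALT as liver-associated enzymes. A generous reading of the term could add ALP and GGT, which are in the same chemistry panel. It would still not reach bilirubin or symptoms.

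**Step 3: whether a bilirubin baseline exists for this purpose.** The table note gives one for ALT only. SAP Section 3.3.7 has a general baseline definition, but it is stated to be for analysis and does not guide sites on restart.

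**Step 4: comparison with the entry standard.** Exclusion criterion 12 bars subjects whose total or direct bilirubin is above the ULN. The exception is total bilirubin in Gilbert's syndrome, and it requires direct bilirubin to be normal. As worded, Table 8 permits re-dosing at more than twice a level that would have barred entry or, in Gilbert's syndrome, with direct bilirubin still doubled.

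**Step 5: whether another rule closes the gap.** The rest of Section 7.9 and Sections 4.7, 8.1 and 8.4 contain no other restart rule. All four rows of Table 8 need raised ALT, so once ALT has recovered, no row acts on bilirubin or symptoms that remain.

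**The case against.** The case on the other side has real substance.

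- *Only if* states necessary conditions. Nothing obliges anyone to restart, and Section 8.1 lets a subject at unacceptable risk be discontinued. This stands, and it is why the conclusion is that the wording permits restart and does not direct it.
- The cause requirement applies to the whole event, including its bilirubin or symptom part, and follows a workup that covers viral, autoimmune, alcoholic and ischemic hepatitis and biliary tract disease. Rechallenge is advised against if DILI is determined. Both limit re-exposure after true DILI. They concern cause, however, and say nothing about recovery.
- Bilirubin is retested under close monitoring, the Medical Monitor should be consulted, laboratory results must be reviewed, and significant abnormalities are followed to resolution. These are real safeguards, but none sets a threshold for restart. Retesting may also become less frequent once abnormalities stabilize, which is not the same as recovery.
- Table 8 follows a cited published algorithm. That explains its form, and the point is therefore an improvement to the rule and not a contradiction within the documents.

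Three stronger readings are tempting, and the documents do not support them.

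- A reader might infer that restart depends on ALT alone. It does not: the enzyme condition takes in at least AST as well, and the cause condition covers the whole event.
- A reader might infer that follow-up of the bilirubin can lapse once another cause is found, because Section 7.8 lists "The AE or SAE is considered not causally related to investigational product" among its end points. Table 6 in Section 7.5 blocks this. Its unrelated category also requires that there be no temporal relationship to the drug, and an event arising on treatment has one. An alternative cause is not enough.
- A reader might infer that nothing in the protocol would respond to persistent bilirubin or symptoms. Step 5 above concerns the rows of the table only; the monitoring and review duties still apply.

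**Conclusion.** The gap is real and narrow. In 2 of 3 interruption rows, the stated restart conditions leave out recovery of the component that caused the interruption. The bilirubin row is the clearer case, because it permits re-dosing with total bilirubin still above twice the ULN.

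This rests on reading liver enzymes as the protocol uses the term and on Table 8 holding the only restart conditions. The study procedures manual and the DSMB charter are not among the documents and could add some.

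The number of subjects affected cannot be calculated because no event rate is given. It is probably small: a subject would need a joint trigger, an identified other cause, recovered enzymes, persisting bilirubin or symptoms, and a decision to restart, all within 18 weeks. No efficacy estimate depends on the point. It is worth making as a cheap improvement to a safety rule.

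**What to change.** - **Row 3:** add that total bilirubin (direct bilirubin in Gilbert's syndrome) has returned to baseline or to normal.
- **Row 4:** add the same bilirubin condition where bilirubin was elevated, and that the triggering liver symptoms have resolved. An exception for symptoms put down to the identified cause is best left out, since it would bring the row nearly back to its present meaning.
- **Table note:** define baseline bilirubin from the Screening and Baseline values.
- **Row 2:** no change.

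The change is wording in two rows and a note. Total and direct bilirubin are already in the Screening and Baseline chemistry panels and in the reduced panels at Weeks 2, 6 and 14, and a symptom history is already taken. No test, visit or subject is added.

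The downside is that a few subjects stay off drug longer or do not restart. For a subject who restarts and completes 18 × 7 = 126 days:

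- **80-day dosing rule (Protocol Section 9.2.2, SAP Section 4.1):** unaffected if days run from first to final dose, as in the SAP definition of days on treatment. If only dosed days count, 126 − 80 = 46 days off drug can be absorbed.
- **80% compliance rule (SAP Section 4.3):** assuming interrupted days stay in the denominator and the subject is otherwise fully compliant, 25 days off gives 101/126 = 80.2% and 26 days off gives 100/126 = 79.4%. A total interruption of 26 days or more would therefore remove the subject from the Per Protocol Set.

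A subject who stops for good before 80 days of dosing leaves the Efficacy set but stays in the Modified Efficacy set if the early termination MRI is done. The present rule already causes part of any such interruption.
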